Infant RSV LRTI hospitalization has been selected as the primary endpoint since hospitalization for LRTI due to RSV is a significant part of RSV burden of disease and the assessment of cases does not impose additional clinical procedures on participants or parents/LARs. The assessment of very severe RSV LRTI cases will be used as one of the main secondary endpoints as it will allow evaluating the impact of nirsevimab on the incidence of RSV infection in its rarer but direst manifestations.

This study's design does not permit blinding. Parents/LARs will know whether their infant received the study intervention or not and, depending on the enrollment setting (eg, hospital or medical office), the child's pediatrician or the family doctor may be the person performing inclusion in the study, administering or not administering the study intervention, and later advising parents/LARs on the course of action in case of respiratory infection. These "real-world" conditions are bound to introduce some bias that the use of a blind assessor or of an adjudicating committee would not entirely alleviate (55). However, and although this study is open-labelled, the selection of a very robust and patient-oriented endpoint kernel (ie, RSV LRTI hospitalization) will allow for a scientifically sound and clinically relevant assessment of nirsevimab efficacy.

Despite being a monoclonal antibody, nirsevimab will be administered by intramuscular injection like routine pediatric vaccinations. Furthermore, nirsevimab can be co-administered along with routine pediatric vaccines planned in the vaccination schedule of each country (53). This will facilitate its administration during routine appointments, making it possible to immunize the entire intervention cohort at the start of the season using existing healthcare appointments when possible. This, in line with the mostly pragmatic study design, will further help minimize the burden on parents/LARs of participants and on the healthcare system of each country.

Rationale for the Study Population

The participants to be enrolled are all infants from France, Germany, and UK, under the age of 12 months entering their first RSV season that are not eligible to receive RSV prophylaxis with palivizumab, which indication is limited to infants with certain underlying conditions such as chronic lung disease, congenital heart disease, or very premature.

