6.8 Concomitant Therapy

The following concomitant reportable medications will be collected:

- Medications that may affect the interpretation of safety data (eg, an antipyretic or analgesic that could have reduced the intensity or frequency of an AE)
- All vaccines administered within 14 days before and after dosing/randomization. It is to be noted that routine childhood vaccines scheduled at the time of the enrollment visit should be administered as planned
- All medications administered within 14 days before and after admission for LRTI hospitalization
- Routine immunization with nirsevimab (Beyfortus). For countries where Beyfortus has been made commercially available during the study conduct, the sites will be asked to report any routine immunization with Beyfortus.

Reportable medications will be collected in the eCRF. Dosage, homeopathic medication, topical steroids, as well as topical, ophthalmic, and ear treatments will not be recorded (except topical analgesics applied at the injection site of study intervention). Inhaled steroids will be recorded only when prescribed during a wheezing episode (see below).

Medications given in response to an AE will be captured in the "Action Taken" section of the AE eCRF.

For UK reconsented participants, the following concomitant medications will be collected:

- Medications related to related SAE and/or LRTI hospitalization
- Any medications prescribed during a wheezing episode.

Medications will be coded using the WHODrug dictionary.

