An adverse reaction (AR) is any noxious and unintended response to a study intervention related to any dose.

All AEs occurring at and around the IMP injection/administration site are to be considered by default as related to the IMP administered at that site and are therefore referred as injection/administration site ARs.

All AEs which are not at and around the IMP injection/administration site, are referred as systemic AE. For each systemic AE, the investigator assesses the relationship to the IMP. Systemic AEs assessed as related to IMP are referred as systemic ARs.

Immediate Event/Reaction:

Immediate events are recorded to capture medically relevant AEs which occur within the first 30 minutes after immunization.

Adverse Event of Special Interest (AESI):

An adverse event of special interest (serious or non-serious) is one of scientific and medical concern specific to the Sponsor's study intervention or program, for which ongoing monitoring and rapid communication by the investigator to the Sponsor can be appropriate. Such an event might warrant further investigation in order to characterize and understand it. Depending on the nature of the event, rapid communication by the study Sponsor to other parties (eg, regulators) might also be warranted.

Medically Attended AE (MAAE)

An MAAE is a new onset or a worsening of a condition that prompts the participant or participant's parent/legally acceptable representative to seek unplanned medical advice at a physician's office or Emergency Department. Physician contact made over the phone or by email will be considered a physician office visit for the purpose of MAAE collection. This includes medical advice seeking during the study visit or routine medical care. This definition excludes pediatric check-ups, follow-up visits of chronic conditions with an onset prior to entry in the study.

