6.7.2. Adverse Events

6.7.2.1. Definitions/ Derivations

All AEs recorded on the eCRF will be coded using the MedDRA dictionary (version 25.0) and classified as treatment-emergent AEs (TEAEs) as follows:

- Pre-treatment AEs are events
 - that start prior to the start of the Treatment Period and with a stop date before the Treatment Period
- or
- with a stop date after the start of the Treatment Period or with a missing stop date, but with a grade lower or equal to 1.
- TEAEs are either events
 - with the start date and time posterior to the start of the Treatment Period and up to the end of the Treatment Period

or

- events with the start date and time prior to the start of the Treatment Period
 - whose severity is greater than 1 or missing
- and
 - stop date is missing or not before the Treatment Period.
- Treatment-Emergent Serious AEs will be defined as TEAEs where Serious = “Yes”
- The relationship between a TEAE and treatment is assessed as related, or not related. A treatment-related TEAE will be defined as a TEAE considered by the investigator as related or, with unknown / missing relationship to treatment for participants who received nirsevimab on Day 1. An unknown / missing relationship between a TEAE and treatment for participants who received no intervention will be considered as not related.
- Assessment of AE intensity will be based on the AEs intensity grading scales adapted from the “FDA Guidance for Industry: Toxicity Grading Scale for Healthy Adult and Adolescent Volunteers Enrolled in Preventive Vaccine Clinical Trials, September 2007”
- TEAEs leading to discontinuation of study are defined as TEAEs where “Caused Study Discontinuation” is indicated as “Yes”.
- Pyrexia includes those adverse events with PT term equal to ‘Pyrexia’.
- Injection site reactions include those adverse events with category of adverse event equal to ‘IMP Injection/Administration Site Reaction’ or ‘Other Vaccination Injection/Administration Site Reaction’.
- Rash includes those adverse events with PT term equal to ‘Erythema’, ‘Rash’, ‘Rash macular’, ‘Rash maculo-papular’ or ‘Urticaria’.

In addition to the aforementioned AE types, TEAEs of special interest will be identified in eCRF (Is the event an AESI = Yes):

- Hypersensitivity, including anaphylaxis
- Immune complex disease
- Thrombocytopenia

Immediate AEs are recorded to capture medically relevant AEs which occur within the first 30 minutes after immunization.

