6.7.2.2. Analyses

Adverse events will be summarized by default descriptive summary statistics for categorical variables for the SafAS by treatment group and overall as follows:

- An overview of TEAEs (#) including the number and percentage of participants with at least one of each mentioned TEAE type provided with 95% Clopper-Pearson confidence interval:
 - Any TEAE
 - Leading to discontinuation of study
 - Leading to death
 - Grade 1 severity
 - Grade 2 severity
 - Grade 3 severity
 - Any study treatment related TEAE
 - Leading to discontinuation of study
 - Leading to death
 - Grade 1 severity
 - Grade 2 severity
 - Grade 3 severity
 - Any serious TEAE
 - Leading to discontinuation of study
 - Leading to death
 - Any serious study treatment related TEAE
 - Leading to discontinuation of study
 - Leading to death
 - Non-serious TEAEs until 30 days after Day 1
 - Leading to discontinuation of study
 - Grade 1 severity
 - Grade 2 severity
 - Grade 3 severity
 - Any immediate TEAEs reported in the 30 minutes after immunization
 - Leading to discontinuation of study
 - Leading to death

- Grade 1 severity
 - Grade 2 severity
 - Grade 3 severity
 - Medically-attended TEAEs
 - Leading to discontinuation of study
 - Leading to death
 - Grade 1 severity
 - Grade 2 severity
 - Grade 3 severity
 - TEAEs of Special Interest
 - Leading to discontinuation of study
 - Leading to death
 - Grade 1 severity
 - Grade 2 severity
 - Grade 3 severity
- The number and percentage of participants reporting each TEAE and the number of events as well as 95% Clopper-Pearson confidence interval will be summarized by SOC and PT for the following types of TEAEs:
 - Non-serious TEAEs through Day 31 post-dosing/randomization (*)
 - Immediate TEAEs reported in the 30 minutes post-dosing/ randomization (*)
 - Medically-attended TEAEs (*) (#)
 - TEAEs of Special Interest (*) (#)
 - TEAEs Leading to Death
 - TEAEs by Maximum Intensity (*) (#)
 - TEAEs by Relationship to Treatment (*) (#)
 - Study Treatment related TEAEs Leading to Death (*)
 - Serious TEAEs (*) (#)
 - Study Treatment Related Serious TEAEs (#)
 - Study Treatment Related TEAEs (*) (#)
- The number and percentage of participants who died will be summarized by the primary cause of death

All AE tables mentioned above will also be repeated for the following subgroups:

- ✓ By country
- ✓ By weight group (< 2.5 kg, < 5 kg, ≥ 5 kg)
- ✓ By age group (neonate participants, randomization stratification)

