In addition, all AE tables by SOC and PT listed above and flagged with (*) will also be repeated in participants who received other vaccines:

- ✓ On the same day as nirsevimab
- ✓ Within 7 days before or after nirsevimab immunization
- ✓ Within 14 days before or after nirsevimab immunization.

For the subgroups about participants who received other vaccines, see [Table 6](#) from Appendix 2 (Section 8.2) to get the vaccines to be considered.

Moreover, below tables will be produced:

- ✓ Non-serious TEAEs through Day 31 post-dosing/randomization by SOC and PT in at least 1% of participants
- ✓ Medically-attended TEAEs by SOC and PT in at least 1% of participants
- ✓ TEAEs through Day 7 post-dosing/randomization by SOC and PT
- ✓ TEAEs through Day 7 post-dosing/randomization by SOC and PT - Pyrexia
- ✓ TEAEs through Day 7 post-dosing/randomization by SOC and PT - Injection Site Reactions
- ✓ TEAEs through Day 14 post-dosing/randomization by SOC and PT
- ✓ TEAEs through Day 14 post-dosing/randomization by SOC and PT - Rash

Study Treatment Related Serious TEAEs tables by SOC and PT (overall and by subgroups) and with the number of events as well as 95% Clopper-Pearson confidence interval will also be produced at the time of Second Year Analysis in UK re-consented participants for the below periods:

- ✓ From 366 Days Post-Dosing/Randomization to 731 Days Post-Dosing/Randomization.
- ✓ From Day 1 to 731 Days Post-Dosing/Randomization
- ✓ From Day 1 to 366 Days Post-Dosing/Randomization

The summary table of TEAE will also be produced at the time of Second Year Analysis in UK re-consented participants for the below periods;

- ✓ From 366 Days Post-Dosing/Randomization to 731 Days Post-Dosing/Randomization.
- ✓ From Day 1 to 731 Days Post-Dosing/Randomization
- ✓ From Day 1 to 366 Days Post-Dosing/Randomization

For the period “From 366 Days Post-Dosing/Randomization to 731 Days Post-Dosing/Randomization”, only below TEAE will be presented:

- TEAE with a start date on or after Day 366,
- TEAE with a start date before Day 366 but ongoing at Day 366 (no stop date or with a stop date after Day 366).

For summaries by maximum intensity, participants with multiple TEAEs within a particular SOC or PT will be counted under the category of their most severe TEAE within that SOC or

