PT. TEAEs with missing intensity will be included in the counts of the ‘Number of Participants with at least one TEAE’, ‘System Organ Class’, and ‘Preferred Term’ rows of the summary but they will not be included in the counts by intensity.

In addition, all AE tables by SOC and PT flagged with (#) as well as the summary table will be repeated in participants who received Beyfortus as a routine medication if there are at least 10 concerned participants.

Summaries by SOCs and PTs will be sorted by SOCs by their Internationally Agreed Order (MedDRA) and PTs within SOC by descending order of total incidence. Where preferred terms tie PTs will be sorted alphabetically.

No statistical comparisons of AEs between treatment groups will be performed.

All AE data will be listed and Pre-treatment AEs and TEAEs will be presented together. Treatment-emergence status will be flagged in the listing. The listing will present the relative start and stop day of the AE calculated relative to the first dose of treatment and will be presented for those participants who received at least one dose of treatment. If the AE is “Ongoing” it will be indicated as such in the listing and the relative stop day will not be calculated. Only original dates will be presented in the listing even though the relative day may be based on an imputed date.

In addition, the following listings will be presented:

- Listing of Deaths
- Listing of Serious TEAEs
- Listing of TEAEs Leading to Discontinuation of Study
- Listing of TEAEs of Special Interest
- Listing of Immediate TEAEs reported in the 30 minutes after immunization
- Listing of Medically Attended AEs
- Listing of all non TEAEs not included in the Safety Analysis
- Listing of all non TEAEs not included in the Safety Analysis in the United Kingdom for Reconsented Participants (only at the time for the Second Year Analysis)
- Listing of all Adverse Events starting before the End of the Treatment Period defined for the First Year Analysis but not included in the First Year Analysis since they were reported after First Year Database Lock in the United Kingdom for Reconsented Participants (only at the time for the Second Year Analysis)

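### The SAP's injection site reaction definition pools the nirsevimab site with other vaccines' sites, so no planned table described in the SAP isolates Day 7 reactions at the nirsevimab site

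*SAP*

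**What the plan says.** **SAP 6.7.2.1** opens its definition with "Injection site reactions include those adverse events with category of adverse event equal to" and then names two eCRF categories joined by the word or. The first is a reaction at the administration site of the investigational product. The second is "Other Vaccination Injection/Administration Site Reaction".

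**SAP 6.7.2.2** uses the definition in one named output: "TEAEs through Day 7 post-dosing/randomization by SOC and PT - Injection Site Reactions". The section says adverse events are summarised "for the SafAS by treatment group and overall as follows". It also says "No statistical comparisons of AEs between treatment groups will be performed".

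**Protocol 10.2.1** uses the term more narrowly: "All AEs occurring at and around the IMP injection/administration site are to be considered by default as related to the IMP administered at that site". Such events are called injection-site adverse reactions. An adverse event away from that site is classed as systemic, and the investigator judges its relationship to the product.

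**Co-vaccination** is expected. Protocol 6.8 notes that "routine childhood vaccines scheduled at the time of the enrollment visit should be administered as planned", and Protocol 4.2 gives as part of the design rationale that "nirsevimab can be co-administered along with routine pediatric vaccines planned in the vaccination schedule of each country".

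**The concern.** Characterising the safety profile of nirsevimab is a secondary objective, and tolerance at the injection site is a natural part of it. Someone who knows the protocol's meaning of the term, and then opens a table titled injection site reactions, would attribute the whole nirsevimab column to nirsevimab. Under the SAP definition that would be wrong for any infant whose only reaction was at the site of a routine vaccine. At stake is how one descriptive table is read. No hypothesis test or protocol-listed endpoint depends on it: the safety endpoints in Protocol section 3 include neither a Day 7 endpoint nor an injection-site endpoint. The Day 7 and Day 14 summaries entered with SAP version 6.0, according to the SAP document history.

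**Working it through.** The plan gives no figure to reproduce. The check sets the passages side by side and follows what the table would count.

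**1. What the nirsevimab column counts.** Among infants who received nirsevimab, let A be those with a product-site reaction through Day 7, and B those with a reaction at another vaccine's site through Day 7. The SAP definition counts infants in A or B:

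count = |A| + |B without A|.

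This is never below |A|. It equals |A| only if every infant in B is also in A. The direction needs no assumption about rates.

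**2. Whether B can be populated.** Yes. Protocol 6.8 has routine vaccines given at the enrolment visit as planned, and that visit is also the dosing visit.

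**3. What the control column counts.** SAP 4.4 analyses safety by the intervention actually received, so a control infant given nirsevimab inadvertently does not sit in the control column. With no study injection, that column can hold only reactions at other vaccines' sites. The overall column combines two different quantities.

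**4. Whether the protocol and SAP agree.** They do not. A reaction at another vaccine's site is a systemic event under Protocol 10.2.1 and an injection site reaction under SAP 6.7.2.1. Neither document reconciles the two.

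**5. Whether another planned output isolates the Day 7 product-site reactions.**
- *Treatment-related TEAEs, and TEAEs by relationship (SAP 6.7.2.2).* Product-site events are related by default, so these tables include them. They are not limited to Day 7 or to local reactions. In nirsevimab recipients they also count events with missing relationship as related (SAP 6.7.2.1).
- *Repeats in co-vaccinated infants (SAP 6.7.2.2).* These apply to tables listed above that sentence and marked with an asterisk. The Day 7 injection site table comes after it and has no mark.
- *Rows by SOC and preferred term.* Nothing in the SAP says that the preferred term identifies which injection site was involved.

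None of these gives the Day 7 nirsevimab-site figure.

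**6. Size.** Let p be the product-site rate, c the share co-vaccinated and v the vaccine-site reaction rate among those co-vaccinated. If the two kinds of reaction are independent:

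pooled rate = 1 − (1 − p)(1 − c·v).

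The documents give none of p, c or v, so the excess over p cannot be derived from them.

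**The case against.** **The table is explicit and has a control column.** The title does not say nirsevimab-site, the definition is written out, and nirsevimab-site reactions are included. Both arms follow the same routine vaccination practice, so the control column shows the vaccine background. The bar on statistical comparisons does not stop a reader setting the columns side by side. Take purely assumed rates of c = 40%, v = 3% and p = 1%. The nirsevimab column reads 1 − 0.99 × 0.988 = 2.19%, the control column reads 1.20%, and the difference of 0.99 percentage points nearly returns p. A pooled event also avoids having to decide which of several same-day injections caused a reaction. This argument largely stands, and it keeps the point minor. Two limits remain. Subtraction is an indirect route to something the eCRF records directly. It also assumes equal reporting in both arms, and Protocol 6.3.2 says that similar attention to the groups cannot be ensured in this open-label study.

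**The layout may already split the categories.** SAP 6.1 leaves table formats to the TFL shells, which are not among the documents. A split by category is possible there, but the SAP text does not promise one.

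**Stronger readings that a reader might infer.** One is that the table fails to report nirsevimab-site reactions. It does report them, mixed with others. Another is that it must overstate them, perhaps several-fold. The count exceeds the nirsevimab-site count only if at least one infant has a vaccine-site reaction alone, and it misleads only a reader who takes the nirsevimab column as a product-site rate. With assumed ranges of 20–60% for c, 1–5% for v and 0.3–1% for p, the ratio of pooled rate to p runs from (1 − 0.99 × 0.998)/0.01 = 1.2 to (1 − 0.997 × 0.97)/0.003 = 11.0. A range that wide reflects the assumptions and is not evidence about this trial.

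**Conclusion.** The point holds as a minor one. The SAP definition is wider than the protocol's, and the nirsevimab column of the Day 7 table can contain reactions at other vaccines' sites. Its count equals or exceeds the nirsevimab-site count by an amount that cannot be sized from the documents. The control column and the related-TEAE tables help a careful reader, but no planned output described in the SAP isolates Day 7 reactions at the nirsevimab site. This rests on two readings: that the Day 7 table follows the by-arm layout stated for SAP 6.7.2.2, and that the TFL shells add no split by category. Efficacy inference is unaffected.

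**What to change.** In SAP 6.7.2.1 and 6.7.2.2:
- Tabulate the two eCRF categories separately in the Day 7 table: product-site reactions among infants dosed with nirsevimab, and other-vaccination-site reactions in both arms.
- If a combined row is kept, label it as pooled across the product's and other vaccines' sites.
- Align the SAP definition with Protocol 10.2.1, either by reserving the term for the product's site or by stating that the SAP uses it more widely, and why.

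The cost is a line of definition and one extra set of rows. The SAP already refers to the two categories as separate values of an eCRF field, so no new data are needed and no other analysis changes.

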6.7.2.2. Analyses

Adverse events will be summarized by default descriptive summary statistics for categorical variables for the SafAS by treatment group and overall as follows:

- An overview of TEAEs (#) including the number and percentage of participants with at least one of each mentioned TEAE type provided with 95% Clopper-Pearson confidence interval:
 - Any TEAE
 - Leading to discontinuation of study
 - Leading to death
 - Grade 1 severity
 - Grade 2 severity
 - Grade 3 severity
 - Any study treatment related TEAE
 - Leading to discontinuation of study
 - Leading to death
 - Grade 1 severity
 - Grade 2 severity
 - Grade 3 severity
 - Any serious TEAE
 - Leading to discontinuation of study
 - Leading to death
 - Any serious study treatment related TEAE
 - Leading to discontinuation of study
 - Leading to death
 - Non-serious TEAEs until 30 days after Day 1
 - Leading to discontinuation of study
 - Grade 1 severity
 - Grade 2 severity
 - Grade 3 severity
 - Any immediate TEAEs reported in the 30 minutes after immunization
 - Leading to discontinuation of study
 - Leading to death

- Grade 1 severity
 - Grade 2 severity
 - Grade 3 severity
 - Medically-attended TEAEs
 - Leading to discontinuation of study
 - Leading to death
 - Grade 1 severity
 - Grade 2 severity
 - Grade 3 severity
 - TEAEs of Special Interest
 - Leading to discontinuation of study
 - Leading to death
 - Grade 1 severity
 - Grade 2 severity
 - Grade 3 severity
- The number and percentage of participants reporting each TEAE and the number of events as well as 95% Clopper-Pearson confidence interval will be summarized by SOC and PT for the following types of TEAEs:
 - Non-serious TEAEs through Day 31 post-dosing/randomization (*)
 - Immediate TEAEs reported in the 30 minutes post-dosing/ randomization (*)
 - Medically-attended TEAEs (*) (#)
 - TEAEs of Special Interest (*) (#)
 - TEAEs Leading to Death
 - TEAEs by Maximum Intensity (*) (#)
 - TEAEs by Relationship to Treatment (*) (#)
 - Study Treatment related TEAEs Leading to Death (*)
 - Serious TEAEs (*) (#)
 - Study Treatment Related Serious TEAEs (#)
 - Study Treatment Related TEAEs (*) (#)
- The number and percentage of participants who died will be summarized by the primary cause of death

All AE tables mentioned above will also be repeated for the following subgroups:

- ✓ By country
- ✓ By weight group (< 2.5 kg, < 5 kg, ≥ 5 kg)
- ✓ By age group (neonate participants, randomization stratification)

In addition, all AE tables by SOC and PT listed above and flagged with (*) will also be repeated in participants who received other vaccines:

- ✓ On the same day as nirsevimab
- ✓ Within 7 days before or after nirsevimab immunization
- ✓ Within 14 days before or after nirsevimab immunization.

For the subgroups about participants who received other vaccines, see [Table 6](#) from Appendix 2 (Section 8.2) to get the vaccines to be considered.

Moreover, below tables will be produced:

- ✓ Non-serious TEAEs through Day 31 post-dosing/randomization by SOC and PT in at least 1% of participants
- ✓ Medically-attended TEAEs by SOC and PT in at least 1% of participants
- ✓ TEAEs through Day 7 post-dosing/randomization by SOC and PT
- ✓ TEAEs through Day 7 post-dosing/randomization by SOC and PT - Pyrexia
- ✓ TEAEs through Day 7 post-dosing/randomization by SOC and PT - Injection Site Reactions
- ✓ TEAEs through Day 14 post-dosing/randomization by SOC and PT
- ✓ TEAEs through Day 14 post-dosing/randomization by SOC and PT - Rash

Study Treatment Related Serious TEAEs tables by SOC and PT (overall and by subgroups) and with the number of events as well as 95% Clopper-Pearson confidence interval will also be produced at the time of Second Year Analysis in UK re-consented participants for the below periods:

- ✓ From 366 Days Post-Dosing/Randomization to 731 Days Post-Dosing/Randomization.
- ✓ From Day 1 to 731 Days Post-Dosing/Randomization
- ✓ From Day 1 to 366 Days Post-Dosing/Randomization

The summary table of TEAE will also be produced at the time of Second Year Analysis in UK re-consented participants for the below periods;

- ✓ From 366 Days Post-Dosing/Randomization to 731 Days Post-Dosing/Randomization.
- ✓ From Day 1 to 731 Days Post-Dosing/Randomization
- ✓ From Day 1 to 366 Days Post-Dosing/Randomization

For the period “From 366 Days Post-Dosing/Randomization to 731 Days Post-Dosing/Randomization”, only below TEAE will be presented:

- TEAE with a start date on or after Day 366,
- TEAE with a start date before Day 366 but ongoing at Day 366 (no stop date or with a stop date after Day 366).

For summaries by maximum intensity, participants with multiple TEAEs within a particular SOC or PT will be counted under the category of their most severe TEAE within that SOC or

PT. TEAEs with missing intensity will be included in the counts of the ‘Number of Participants with at least one TEAE’, ‘System Organ Class’, and ‘Preferred Term’ rows of the summary but they will not be included in the counts by intensity.

In addition, all AE tables by SOC and PT flagged with (#) as well as the summary table will be repeated in participants who received Beyfortus as a routine medication if there are at least 10 concerned participants.

Summaries by SOCs and PTs will be sorted by SOCs by their Internationally Agreed Order (MedDRA) and PTs within SOC by descending order of total incidence. Where preferred terms tie PTs will be sorted alphabetically.

No statistical comparisons of AEs between treatment groups will be performed.

All AE data will be listed and Pre-treatment AEs and TEAEs will be presented together. Treatment-emergence status will be flagged in the listing. The listing will present the relative start and stop day of the AE calculated relative to the first dose of treatment and will be presented for those participants who received at least one dose of treatment. If the AE is “Ongoing” it will be indicated as such in the listing and the relative stop day will not be calculated. Only original dates will be presented in the listing even though the relative day may be based on an imputed date.

In addition, the following listings will be presented:

- Listing of Deaths
- Listing of Serious TEAEs
- Listing of TEAEs Leading to Discontinuation of Study
- Listing of TEAEs of Special Interest
- Listing of Immediate TEAEs reported in the 30 minutes after immunization
- Listing of Medically Attended AEs
- Listing of all non TEAEs not included in the Safety Analysis
- Listing of all non TEAEs not included in the Safety Analysis in the United Kingdom for Reconsented Participants (only at the time for the Second Year Analysis)
- Listing of all Adverse Events starting before the End of the Treatment Period defined for the First Year Analysis but not included in the First Year Analysis since they were reported after First Year Database Lock in the United Kingdom for Reconsented Participants (only at the time for the Second Year Analysis)

Moreover, a complete listing of all adverse events will also be performed at the time of First Year Analysis and Second Year Analysis (but not for the Primary Analysis) in the All Screened Set in addition to the one in the Safety Analysis Set in order to present all AEs that occur in participants who are not in the Safety Analysis Set because they were randomized to nirsevimab group but were not injected.

Listing of AE in the Safety Analysis Set will also be repeated in participants who received Beyfortus as a routine medication at the time of the First Year Analysis.

